4.3.2. Completeness of case ascertainment

4.3.2.1. Prevalent cases

A distinct advantage of using health plan membership and a broad method of initial case identification as the study denominator, versus census data, is greater certainty of

complete ascertainment. However, a possibility exists that cases may be missed. A capture-recapture method will be used to verify the completeness of case ascertainment.

The primary method will be to identify all of the physicians who have treated validated cases. All physicians treating 3 or more validated cases will be sent a letter asking them to compare lists of validated study cases to their cases of eligible patients (within age range, diagnosed with diabetes and residing on Oahu). They will be requested to contact this group if cases are missed. We anticipate a small group of physicians seeing large numbers of children/youth with diabetes and certain offices will be better able to identify cases than others. Focus will be on practices with relatively larger numbers of cases and better information systems. We will request the health plan of missed cases as an indication of other health plans to be considered as supplemental data sources for inclusion in initial case finding.

A second method will be to utilize the Hawaii Health Information Corporation, which maintains a statewide list of all hospital discharges in the state. We will request a listing of all eligible patients with date of birth, date of discharge during index year, gender, health plan and zip code (names are not available). This list will be compared to initially identified cases from health plan data sources assessing whether cases have been missed. Again, this information will serve as an indication of other health plans to consider as supplemental data sources for inclusion in initial case finding.

In addition, we will contact diabetes educators and school nurses to determine if this method yields new cases meeting study criteria.

4.3.2.2. Incident cases

Administrative claims data and Kaiser Diabetes Registry data for the index year (2002) and the previous year (2001) will be used to ascertain completeness of network reporting. Theoretically, incident cases should appear in the index year and not in the previous year. All such cases will be compared to those obtained through network reporting. In conjunction with health plan Co-Investigators, treating physicians of patients appearing only in the index year of administrative data and not appearing on the network reporting list, will be contacted for confirmation as an incident case. It is anticipated these cases may include individuals who recently moved to Hawaii and prevalent cases having no health care utilization during the year prior to the index year. This process will enable estimation of the accuracy of using administrative data alone for the identification of incident cases.

4. Methods: Case Ascertainment - Children's Hospital Medical Center, Cincinnati, Ohio

Cincinnati Children's Hospital Medical Center (CCCHMC) is the only pediatric healthcare facility serving southwest Ohio, northern Kentucky, and southwest Indiana. As a result, children and adolescents with complex medical problems are referred almost exclusively to CCCHMC. The majority of patients served by CCCHMC are residents of one of eight counties surrounding the hospital. These eight counties make up the primary service area for the hospital.

GOAL

The goal in Cincinnati is to ascertain and validate all unique (non-duplicated) cases of diabetes in youth less than 20 years of age in the 8-county primary service area for CCCHMC. This will allow estimation of prevalence and incidence rates by age, gender, and race/ethnicity.

4.1. DENOMINATOR DETERMINATION

Prevalence of diabetes in youth less than 20 years of age was estimated for the year 2001 in the 8-county primary service area for CCCHMC. July 2001 age and gender specific projections derived from Census 2000 data for these 8 counties were used to determine the prevalence denominator. Since these 8 counties do not encompass any military installations, it was not necessary to adjust projections to compensate for military personnel in the denominator. Race data for the following racial/ethnic groups was based on the race-bridging modeling approach developed by the National Center for Health Statistics: Non-Hispanic White, African-American, Hispanic, Asian/Pacific Islander, and Native American/Alaska Native. In addition, zip code level geocoding was used to assign race to prevalent cases for whom race data was unknown (6).

4.1.1. Site specific approaches

The geographic area to be used as the denominator for the calculation of prevalence and incidence will include the 8-county primary service area for CCCHMC. These counties include:

Ohio – Butler, Clermont, Hamilton, and Warren Counties
Kentucky – Boone, Campbell, and Kenton Counties
Indiana – Dearborn County

4.1.2. Denominators for prevalence

The following tables summarize projections from Census 2000 data on July 1, 2001 for the 8-county primary service area of CCHMC. A race-bridging model and zip code level geocoding were used to arrive at the race/ethnicity specific totals.

Characteristic	Population Denominators (%)
Total population	549,356
Age group	
0 – 4 years	132,995
5 – 9 years	135,708
10 – 14 years	143,334
15 – 19 years	137,319

Gender	
Male	280,744
Female	268,612
Race/ethnicity	
Non-Hispanic White	445,009
African-American	86,296
Hispanic	8,204
Asian/Pacific Islander	8,659
American Indian	1,188

4.1.3. Denominators for incidence

Incidence of diabetes in youth less than 20 years of age will be estimated in the years 2002, 2003, and 2004 in the same 8-county primary service area used for prevalence calculations. Incidence denominators will be determined using projections for the index year based on Census 2000 data. Race/Ethnicity will be assigned using the same bridging and geocoding methods.

4.2. CASE ASCERTAINMENT

4.2.1. Prevalent Cases

4.2.1.1. Case finding site-specific approaches

Primary Source for Case Identification

The primary source for identification of prevalent cases was the Diabetes Database, maintained by the Division of Endocrinology at CCCHMC. In 1988 a clinical database of diabetes patients seen at CCCHMC since 1978 was established by review of their medical records. This database continues to be updated on a regular basis.

Patients who live in the 8-county primary service area of CCHMC were identified via their zip codes. All patients who met the eligibility criteria for prevalent cases were contacted to verify that they lived in the 8-county geographic area during the index year. Patients who attended college and lived outside the geographic area during the index year as indicated on IPS were excluded.

The following is a description of the components of the Diabetes Database:
All Diabetes patients both inpatient and outpatient

- a) Demographics
medical record number, name, date of birth, gender, race/ethnicity, home address and home phone, and parents' names and work phones
- b) Clinical information
type of diabetes, date of onset of diabetes, date of most recent diabetes visit to CCHMC, who provided care at each visit, HgbA1c, goals, severe blood sugar episodes and a description of the episode, whether a blood glucose record was kept, co morbidities, insulin or oral agent prescribed.
- c) Physical examination
Date of visit, height, weight, BMI, blood pressure, presence of acanthosis, Tanner stage.

Expanded Sources for Case Identification

Expanded case identification was done to identify subjects who met the eligibility criteria, yet who have never been seen at CCHMC. We have established a network to identify these cases. The following sources yielded the most cases:

- a) Endocrinologists:

There are a total of thirty-one endocrinologists who practice in our 8 county primary service area. Eight of these are pediatric endocrinologists and all eight are employed by CCHMC. Their patients are captured by data dumps from the CCHMC Diabetes Database. The other twenty-three endocrinologists are adult-focused representing fourteen practices. All of these practices were contacted. Two indicated that they do not see clients with diabetes; three do not see youth. Of the remaining practices, one indicated they were unable to generate a list, five provided a list, and three declined to participate.

- b) Hospitals

After Endocrinologists, hospitals identified the largest number of valid, eligible cases. There are eighteen adult-focused hospitals located within the Cincinnati area. These hospitals include: Bethesda North, Christ, Deaconess, Dearborn County, Fort Hamilton, Good Samaritan, Jewish, McCullough-Hyde Hospital, Mercy Hospital Anderson, Mercy Franciscan Hospital Western Hills, Mercy Franciscan Hospital Mt. Airy, Mercy Hospital Clermont, Mercy Hospital Fairfield, Middletown Regional Hospital, St. Elizabeth, St. Luke Hospital East and West, and University Hospital. In addition, one pediatric hospital, Children's Medical Center in Dayton, OH, provides care for young people in our catchment area. Approval was received from 7 IRB's and 7 Oversight Committees. One IRB Services Agreement was signed. Initially, all hospitals were asked to identify all inpatients and outpatients born after 12/31/1981 who were assigned a diagnostic code of 250.xx and had a visit after January 1, 2000. Sixteen hospitals complied with our request. Two passively refused. One hospital services an older population and after querying their system did not have any cases that met our eligibility requirements. Once approvals were in place, lists were generated

on a regular basis adjusting the visit date to correspond to the date queried on the previous list.

c) Additional Secondary sources included:

Certified Diabetes Educators (CDE's)

Members of the Diabetes Educators of the Cincinnati Area, a local organization for diabetes educators, had agreed to participate in our network for the identification of cases. Their membership consists primarily of registered nurses and dietitians. Following the implementation of HIPAA, several of the educators contacted were reluctant to provide us with names of clients with diabetes. A small number of CDE's working in endocrine or primary care offices were contacted to aid with validation. A majority of the CDE's associated with hospital educational programs did provide the names of young people with diabetes for whom they provided services.

Private and Public Payors

Four major private insurance companies serve the majority of the Cincinnati area population. At the time of our original grant proposal, three of four companies had agreed to assist us in the identification of cases. After HIPAA was implemented, collecting data from these providers became more problematic. Anthem, Humana, United Health Care and Aetna were contacted. Of these payors, Anthem and Aetna provided data.

Four state or federally funded programs serve Cincinnati area clients. All four were contacted. The Bureau for Children with Medical Handicaps (BCMh) required Ohio Department of Health IRB approval. Approval was granted, however, we did not receive the requested information from BCMh. OH Medicare refused to release data. Caresource HMO (a version of Medicaid) did provide a list. Kentucky Medicaid did report cases based on ICD-9 code; however, we were unable to validate "new" cases, because charts were unavailable and provider name was omitted. The Kentucky Commission for Children with Special Health Care Needs was contacted, but reported that they did not provide services for children with diabetes.

City and State Health Departments

The City of Cincinnati Health Department and the Ohio Department of Human Services originally agreed to participate in our network to identify cases. We received IRB approval and the Cincinnati Health Department provided data. Chart reviews were completed to validate "new" cases and collect core information. The Boone County (KY) Health Department Diabetes Coordinator stated she rarely sees children or young adults and had no names to report.

Colleges and Universities

The health centers of the four universities with the largest enrollment in our catchment area were contacted about providing data. All four stated health forms were not a requirement, and therefore, unless students presented with a problem related to their diabetes or were frequent visitors with unrelated conditions and remembered by the staff, identification would be impossible. Miami University did agree to provide names and core data on students with diabetes known to them. The Medical director called each student and obtained individual authorization to release information to us. The head nurse at Northern Kentucky University's Health Center offered to explore the possibility of putting a notice in an on-line student newsletter. The University of Cincinnati agreed to post a flier and to ask students presenting with either a primary or secondary diagnosis of diabetes to complete an IPS.

Other Activities

In addition, we sent a mailing to a sample of primary care physicians (pediatrics, family practice, general practice, and internal medicine) to test the sensitivity of our case-finding methods utilizing our Diabetes Database and our network of partners. We asked this sample of physicians to indicate whether or not they had seen any diabetes patients who meet the eligibility criteria without making a referral to CCHMC or an adult endocrinologist. Since our sampling indicated a number of Family Practitioners treated their own clients with diabetes, we expanded our network and attempted to contact all Family Practitioners. We used the practice or office manager as the initial contact person in each practice. We also publicized this study by attending diabetes walks and programs geared to school nurses. Fliers were distributed to school nurses.

Pursuing the sources listed under section c) was time consuming and yielded a very small number of "new", valid, eligible cases. Therefore, the decision was made to eliminate these sources from future case ascertainment efforts.

Expanded Sources Case Validation and Registration

In order to protect patient confidentiality, lists provided by network providers included the minimum amount of PHI required to de-duplicate cases and collect core data. Anticipating HIPAA issues, we obtained a waiver of individual authorization from the IRB at CCHMC prior to initiating requests for lists to expedite data collection from providers outside of the hospital. We were successful with most providers in using the provisions of 45 CFR §164.512(i) with regards to the use of one IRB approved waiver for covered entities in multisite projects. One of the hospitals did not have an internal IRB, and therefore required an IRB Services Agreement giving CCHMC's IRB authority for our project at their site.

We compared the information provided by outside providers to our Diabetes Database to identify new cases, as well as duplicates. If a medical record was available on a new case, it was reviewed either by a representative of the outside provider or by a SEARCH Study team member to validate and determine eligibility of the case. In situations where a record was not available such as an insurance provider, the physician of record was asked to validate the case.

Most of our network partners agreed to mail information about this study including an IPS to all newly identified cases. Before returning the completed survey, subjects were asked to check a box on the cover of the survey indicating whether or not they wished to be contacted with additional information on the study. They were contacted only if they indicated a desire to receive more information.

New cases were assigned a unique identification number. A limited amount of data including; date of birth, date of diagnosis, type of diabetes, race, gender, county and zip code was added to the SEARCH database under the ID number. Name was assigned as either Jane or John Doe depending on the gender. If the survey was returned, the subject's name and all contact information were added to the database.

The source(s) of each validated case was recorded, i.e. Diabetes Database within CCHMC, endocrinologist, insurance company, school nurse, etc. This information was then used to determine the capture-recapture estimates for completeness of ascertainment.

The IPS completion rate for sources identified outside of CCHMC was approximately 30%.

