4.4.2. Incident cases

Capture-recapture methods will be used for incident cases as they were for prevalent cases. The primary source will be provider reported cases, and the secondary source will be hospital discharge records. Additional sources, such as diabetes educator's lists may also be used as a secondary source.

At 24 - month intervals medical databases will be queried for cases that were not reported by the network of providers during the onset period to increase completeness of case ascertainment. This will be done using the same methods as for prevalent cases

The primary care practice survey will also inform incident case identification.

Death certificate searches will be conducted every 2 years.

APPENDIX 1

Sources of prevalent cases SEARCH-WRDY

Colorado counties: Denver, Adams, Arapahoe, Douglas, Jefferson, Boulder. For capture-recapture estimates, each unduplicated case will record all the sources in the six counties where it was identified.

Source	Type	Record system	Case finding	Validation
Barbara Davis Center (BDC) for Childhood Diabetes	Pediatric Endocrinology	Computerized case records; includes Children’s Hospital cases; many of KP cases up to age ~ 16; Denver Health cases	Search of clinical computerized database (excluding codes for “rule out” diabetes; sibling); ICD codes not used in database	Review of all possible cases by responsible BDC provider, using name, date of birth, and computerized record contents (visit content, current treatment, etc.); record review in selected cases.
Kaiser Permanente	HMO	Computerized diabetes registry based on validated (adult) algorithm	Diabetes registry using computer algorithm: [(Pharmacy: Hedis medications + Chemstrips minus glucagon prescriptions) plus (Inpatient and outpatient codes: ICD 250.XX) plus (Lab: none)]	Presence in BDC database or chart review KP validation results: Sens=93.3%, Spec=100%; Accuracy= 99.5%; PPV+=100%; PPV- = 99.5%
Denver Health	HMO/ Community Health Center	Computerized diabetes registry; not well studied	Diabetes registry using computer algorithm: ICD codes 250.XX. Exclude: gestational diabetes (648.8); hyperglycemia NOS (790.6), neonatal diabetes mellitus(775.1), nonclinical diabetes (790.2)	Presence in BDC database or Denver Health chart review
Pediatric endocrine practice:	Private practice	Chart	Chart review	Simultaneous chart review

Source	Type	Record system	Case finding	Validation
[name]				

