Prevalent cases of diabetes will also be identified through the Group Health Diabetes Registry. This registry has been available at Group Health Cooperative of Puget Sound, a not-for-profit HMO that serves more than 400,000 enrollees in Western Washington, since 1995-1996. Patients with diabetes are identified from administrative databases by pharmacy (insulin or diabetes medications), laboratory (elevated fasting or random blood glucose levels or elevated HgbA1c levels) or hospital discharge data (ICD-9 codes for diabetes mellitus). Utilization and laboratory data are added regularly to keep this registry database current. [Ref McCullough DK et al. A Population-Based Approach to Diabetes Management in a Primary Care Setting. *Effective Clinical Practice*. 1998;1:12-22]

g) Washington State Comprehensive Hospital Abstract Reporting System (CHARS)

A secondary data source that will be used for identification of hospitalized diabetes cases is the Washington State Comprehensive Hospital Abstract Reporting System (CHARS). While CHARS will not be used to identify prevalent cases, it will be used to identify hospitals that admit youth with diabetes and to assess the comprehensiveness of case ascertainment.

CHARS will be used to retrospectively examine first time hospitalizations (new diagnoses) for diabetes (ICD-9 CH 250.xx) among youth aged less than 20 years. In a preliminary examination of CHARS data for incident cases of diabetes in youth under age 20, 30% of the hospitalizations took place at CHRMC, 17% at MBCH. Every other hospital in the state provided the initial admission for less than 5% of the incident cases of diabetes in youth less than 20 years of age. It is estimated that 70% of incident cases of type 1 diabetes in the youth (particularly the very young and those with severe diabetic ketoacidosis) are managed in the inpatient setting and thus captured through hospital-based admissions/discharge data sources. Youth with severe diabetic ketoacidosis and very young children are generally admitted to the pediatric tertiary-care hospitals, CHRMC or MBCH. These data can be evaluated for the Puget Sound region counties of study and compared to the known cases from the clinical sites.

h) Insurance administrative data

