4.4.2. Completeness of case ascertainment

4.4.2.1. Prevalent cases

Capture-recapture

Capture-recapture methods will be used to calculate the completeness of case ascertainment. The best statistical methods will be used, incorporating multiple primary ascertainment sources (e.g. endocrinologist, primary care provider, CHARS, etc.), with adjustment for non-independence of data sources. Cases from Group Health will be excluded from capture-recapture methodology given the non-independence of data sources from that institution.

Data elements required to calculate capture-recapture estimates:

- Source of case record
- Date of inclusion on data source
- Record numbers to remove duplicates from same data source.

Random sample of primary care practices

Extensive case identification from a random sample of primary care practice will also be used to estimate the completeness of case ascertainment.

Death certificates

Information from death certificates on individuals with diabetes listed as cause of death will be requested from the state department of Vital Statistics. This information

will be matched against local SEARCH database to further assess completeness of case ascertainment. Cases identified using only death certificates will be classified as death-certificate-only cases.

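### Cincinnati's capture-recapture can keep a payor list's matched records while losing its unmatched ones that could not be validated, which overstates completeness by an unknown amount

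*Protocol*

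**What the plan says.** All of the following is in the protocol's Cincinnati section unless another place is named.

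- **Matching comes first** (4.2.1.1, Expanded Sources Case Validation and Registration): "We compared the information provided by outside providers to our Diabetes Database to identify new cases, as well as duplicates".
- **Only unmatched records then need validation** (same place): "If a medical record was available on a new case, it was reviewed either by a representative of the outside provider" or by a study team member. Where no chart existed, as with insurers, the physician of record was asked.
- **Database cases are already confirmed.** Section 4.3.1.1 has their medical records reviewed before registration.
- **Kentucky Medicaid** (4.2.1.1, Private and Public Payors) reported cases by diagnosis code. Its new cases could not be validated "because charts were unavailable and provider name was omitted", so both validation routes were closed.
- **Use of the sources**: "The source(s) of each validated case was recorded, i.e. Diabetes Database within CCHMC, endocrinologist, insurance company, school nurse, etc". Then: "This information was then used to determine the capture-recapture estimates for completeness of ascertainment". No source is excluded. Section 4.3.1.2 plans the same for incident cases, and 4.2.2.1 lists insurance companies among the partners used for 2002 and 2003.
- **Planned adjustment**: sections 4.3.1 (general) and 8.1.1 adjust for dependence between sources. They do not address validation that depends on the match.

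**The concern.** Capture-recapture estimates what the primary list missed from second-list records that the primary list does not contain. Here the chance that a true case stays in the table depends on whether it matched. A matched record inherits the hospital's confirmation, while an unmatched one needs a chart or a named physician. For a source that offers neither, matches count as recaptures and misses disappear.

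Section 4.3 treats complete ascertainment as critical to the validity of the rates, and capture-recapture is the main formal check on it. A figure biased upward would reassure where reassurance is not earned. The cases hidden would be those known only to a payor. Three of the eight counties are in Kentucky.

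There is a side effect. Cincinnati dropped its additional secondary sources, payors included, because they yielded few new, valid, eligible cases. For Kentucky Medicaid, a low yield reflects the inability to validate and says nothing about how many cases were missed.

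**Working it through.** The protocol gives no capture-recapture estimate, list count or validation rate for Cincinnati, so there is no completeness figure to reproduce. The check is algebra plus illustration.

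**Inputs**
- From the document: v = 0 for Kentucky Medicaid's unmatched records; v above 0 for sources with charts; 1,036 expected prevalent cases (Table 3-1), used for scale only.
- Assumed: primary-list coverage p, second-list coverage c, and v for the other sources. Lists are taken as independent.

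**Formula.** With N true cases, matched m = N·p·c and true unmatched u = N·(1 − p)·c. The two-list (Lincoln-Petersen) estimate of primary-list completeness is m/(m + u) = p. If a fraction v of the true unmatched cases survives validation, it becomes

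m/(m + v·u) = p/(p + v·(1 − p)).

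This is never below p, does not depend on c, and equals 1 when v = 0.

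**Example.** For p = 0.90, c = 0.30, v = 0.5: m = 1,036 × 0.90 × 0.30 = 279.7 and u = 1,036 × 0.10 × 0.30 = 31.1. The estimate is 279.7/(279.7 + 15.5) = 94.7% against a true 90%.

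| True coverage | v = 1 | 0.75 | 0.5 | 0.25 | 0 |
|---|---|---|---|---|---|
| 80% | 80.0 | 84.2 | 88.9 | 94.1 | 100 |
| 90% | 90.0 | 92.3 | 94.7 | 97.3 | 100 |
| 95% | 95.0 | 96.2 | 97.4 | 98.7 | 100 |

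**Does the dependence adjustment help?** No. In the three-list log-linear model without the three-way term, the unseen cell is n111·n100·n010·n001/(n110·n101·n011). It is proportional to the count seen only by the second list (n010). With coverages 0.9, 0.2 and 0.2, losing half of that cell gives an estimated completeness of 96.7% against a true 92.8%. Losing all of it gives 100% against 92.0%.

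**A mixed second list, closer to Cincinnati.** Assume p = 0.90, c = 0.20, Kentucky Medicaid supplying 15% of second-list coverage with v = 0, and v = 0.9 elsewhere.
- Pooled v = 0.85 × 0.9 = 0.765.
- m = 186.48, u = 20.72, v·u = 15.85.
- Primary-list completeness: 186.48/202.33 = 92.2%, true 90%.
- All lists together: estimated N = 932.4 × 202.33/186.48 = 1,011.65. Completeness is 948.25/1,011.65 = 93.7%, against a true 948.25/1,036 = 91.5%.
- With a Kentucky Medicaid share of 5%, v = 0.855 and the primary-list figure is 0.9/0.9855 = 91.3%. With 30%, v = 0.63 and it is 0.9/0.963 = 93.5%.

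**Effect of the remedy in the same example.** Excluding Kentucky Medicaid leaves m = 158.51 and 15.85 confirmed unmatched cases: 158.51/174.36 = 90.9%. Weighting the confirmed count by 1/0.9 gives 17.61 and 158.51/176.12 = 90.0%, the true value.

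**The opposite error.** If every unmatched record is counted as a case and half are not cases, a true 90% reads 0.9/(0.9 + 0.2) = 81.8%. One-sided bounds would therefore mislead too.

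**The case against.** Several counter-arguments have weight.

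- **Unvalidated records should not count as cases.** That is right for the numerator. The fault lies in crediting a source's matches while losing its unmatched true cases. Section 4.4 does not cover this, because it registers validated cases with unconfirmed eligibility.
- **Other lists worked.** This stands. Hospitals gave the largest number of valid, eligible cases after endocrinologists, and Health Department charts were reviewed. A reader might infer that Cincinnati's completeness is 100% by construction. The text does not support that, since it would need v = 0 on every second list.
- **It is not stated that Kentucky Medicaid matches entered the table.** True; it is inferred from a rule that excludes no source.
- **The source is already gone.** For 2004 incident cases, 4.2.2.1 narrows the network and drops payors. The point therefore concerns 2001 prevalent cases, and 2002–2003 incident cases where the same payor lists were used.
- **The rates are untouched.** Nothing in the protocol corrects prevalence or incidence by capture-recapture, and 8.1.1 only assesses completeness. A reader should not infer that the rates themselves are miscalculated. Other checks also exist, including the physician mailing and observed-to-expected ratios.
- **Colorado.** Appendix 1 accepts "Presence in BDC database or Denver Health chart review" for Denver Health, and similar routes elsewhere. One might infer that unmatched cases are lost there as well. That is not shown: Colorado 4.2.1.1 allows potential cases to be contacted for validation and accepts self-report, and no passage says charts were unavailable.
- **Seattle.** The Puget Sound section says "While CHARS will not be used to identify prevalent cases, it will be used to identify hospitals that admit youth with diabetes", yet 4.4.2.1 speaks of "incorporating multiple primary ascertainment sources (e.g. endocrinologist, primary care provider, CHARS, etc". One might infer that a CHARS-only case can never enter the table. Section 4.4.2.2 points the other way for incident cases: database counts serve as the denominator to which enrolled cases are matched, so unmatched records remain in the comparison.

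**Conclusion.** The point holds for Cincinnati. Validation depends on the match, at least one source had unmatched records that could not be validated, and no rule removes that source's matches. If they are in the table, completeness is overstated, and adjusting for list dependence does not repair it.

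The size is unknown, because the number of true cases among the unvalidated records is not given. The mixed-list example gives about 2 points; its coverages, the Kentucky Medicaid share, v = 0.9 elsewhere and list independence are all assumptions. At Colorado the bias is possible but not shown. At Seattle there is only a wording conflict to reconcile.

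**What to change.** In Cincinnati 4.3.1.1 and 4.3.1.2, and in the general section 4.3.1:

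1. Exclude from the capture-recapture table, matches included, any source whose unmatched records could not be validated. At Cincinnati this is Kentucky Medicaid.
2. For each remaining source, tabulate matched, confirmed-unmatched, rejected and unvalidatable-unmatched records. Weight the confirmed-unmatched count by 1/(share of unmatched records that could be reviewed). State the assumption that unreviewed records are as likely to be true, eligible cases as reviewed ones.
3. Report completeness bounds with the unvalidatable unmatched records treated as all true cases and as none.

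Apply the same tabulation at Colorado wherever presence in the BDC database counts as validation. In the Puget Sound section, reconcile 4.3.1.1(g), 4.4.2.1 and 4.4.2.2 on how unmatched CHARS records are handled.

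The cost is protocol wording and a re-tabulation of lists and review outcomes that the sites already handle. Stated completeness becomes somewhat less favourable and its interval wider.
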